4.2 Treatment Status of Leuplin PRO

Patients included Safety population

in analysis:

Analysis items:	Full-treatment status of Leuplin PRO	[Yes, no]
	Injection site	[Extensor surface of the upper arm, deltoid region of the upper arm, abdomen, buttocks, other]

Analysis methods: For the aforementioned analysis items, frequency tabulation will be performed.

4.3 Presence or Absence of and Reason for Discontinuation of Observation

Patients included Safety population

in analysis:

Analysis items:	Presence or absence of discontinuation of observation	[No, yes]
	Reason for discontinuation of observation	[Patient's failure to visit the hospital such as transfer to another hospital, death, other]

Analysis
methods:

For the aforementioned analysis items, frequency tabulation will be performed.

5 Matters on Safety

5.1 Occurrence of Adverse Events and Adverse Drug Reactions/Infections

5.1.1 Occurrence of Adverse Events

Patients included Safety population

in analysis:

Analysis item: AEs

Analysis methods: For the aforementioned analysis item, analysis will be performed as described below.

- (1) Number of patients with an AE
- (2) Number of AE
- (3) Proportion of patients with an AE
- (4) Type of AE

For each analysis, events or patients will be counted as described below.

[Number of patients with an AE]

- Number of patients who experienced an AE

[Number of AE]

- Number of reported AE. Multiple episodes of the same AE in the same patient will be tabulated as the total number of episodes.

[Proportion of patients with an AE]

- The proportion of patients with an AE will be calculated as number of patients with an AE/number of patients included in safety evaluation $\times 100$.

[Type of AE]

- AEs will be coded using the MedDRA/J. AEs will be classified by SOC and then tabulated by PT. For the SOC of investigations, AEs will be sorted by HLG (lined up in ascending order of HLG code, but not output) and then tabulated by PT.
- For SOC, the number and proportion of patients with an AE will be listed in internationally agreed SOC order. Multiple episodes of the same SOC in the same patient will be counted as 1 patient for the relevant SOC.
- For PT, the number and proportion of patients with an AE will be listed in ascending order of PT code. Multiple episodes of the same PT in the same patient will be counted as 1 patient for the relevant PT.

5.1.2 Occurrence of Adverse Drug Reactions/Infections

Patients included Safety population

in analysis:

Analysis item: ADRs, etc.

Analysis For the aforementioned analysis item, analysis will be performed as described

methods: below.

- (1) Number of patients with an ADR, etc.
- (2) Number of ADR, etc.
- (3) Proportion of patients with an ADR, etc.
- (4) Type of ADR, etc.

For each analysis, events or patients will be counted as described below.

[Number of patients with an ADR, etc.]

- Number of patients who experienced an ADR, etc.

[Number of ADR, etc.]

- Number of reported ADR, etc. Multiple episodes of the same ADR, etc. in the same patient will be tabulated as the total number of episodes.

[Proportion of patients with an ADR, etc.]

- The proportion of patients with an ADR, etc. will be calculated as number of patients with an ADR, etc./number of patients included in safety evaluation $\times 100$.

[Type of ADR, etc.]

- ADRs, etc. will be coded using the MedDRA/J. ADRs, etc. will be classified by SOC and then tabulated by PT. For the SOC of investigations, ADRs, etc. will be sorted by HLG (lined up in ascending order of HLG code, but not output) and then tabulated by PT.
- For SOC, the number and proportion of patients with an ADR, etc. will be listed in internationally agreed SOC order. Multiple episodes of the same SOC in the same patient will be counted as 1 patient for the relevant SOC.
- For PT, the number and proportion of patients with an ADR, etc. will be listed in ascending order of PT code. Multiple episodes of the same PT in the same patient will be counted as 1 patient for the relevant PT.

**5.1.3 Occurrence of Adverse Events Corresponding to Important Identified Risks
(tabulation by risk)**

Patients included Safety population

in analysis:

Analysis item: AEs corresponding to important identified risks (described in Section 1.4 in Section 1, “Definitions of Terms, etc.”)

Stratification factors: Seriousness [Serious, not serious]

factors:

Analysis methods: For the aforementioned analysis item, analysis will be performed for each stratum by risk as described below. The risks to be analyzed are as described in Section 1.4 in Section 1, “Definitions of Terms, etc.”

[Type of AE]

- AEs will be coded using the MedDRA/J. AEs will be classified by SOC and then tabulated by PT. For the SOC of investigations, AEs will be sorted by HLGTT (lined up in ascending order of HLGTT code, but not output) and then tabulated by PT.
- For SOC, the number and proportion of patients with an AE will be listed in internationally agreed SOC order. Multiple episodes of the same SOC in the same patient will be counted as 1 patient for the relevant SOC. However, when these episodes differ in seriousness, they will be counted once each for “serious” and “not serious.”
- For PT, the number and proportion of patients with an AE will be listed in ascending order of PT code. Multiple episodes of the same PT in the same patient will be counted as 1 patient for the relevant PT. However, when these episodes differ in seriousness, they will be counted once each for “serious” and “not serious.”

5.1.4 Occurrence of Adverse Events Corresponding to Important Potential Risks (tabulation by risk)

Patients included Safety population

in analysis:

Analysis item: AEs corresponding to important potential risks (described in Section 1.4 in Section 1, “Definitions of Terms, etc.”)

Stratification Seriousness [Serious, not serious]

factors:

Analysis For the aforementioned analysis item, analysis will be performed for each
methods: stratum by risk as described below. The risks to be analyzed are as described in Section 1.4 in Section 1, “Definitions of Terms, etc.”

[Type of AE]

- AEs will be coded using the MedDRA/J. AEs will be classified by SOC and then tabulated by PT. For the SOC of investigations, AEs will be sorted by HLG (lined up in ascending order of HLG code, but not output) and then tabulated by PT.
- For SOC, the number and proportion of patients with an AE will be listed in internationally agreed SOC order. Multiple episodes of the same SOC in the same patient will be counted as 1 patient for the relevant SOC. However, when these episodes differ in seriousness, they will be counted once each for “serious” and “not serious.”
- For PT, the number and proportion of patients with an AE will be listed in ascending order of PT code. Multiple episodes of the same PT in the same patient will be counted as 1 patient for the relevant PT. However, when these episodes differ in seriousness, they will be counted once each for “serious” and “not serious.”

5.1.5 Occurrence of Adverse Drug Reactions/Infections Corresponding to Important Identified Risks (tabulation by risk)

Patients included Safety population

in analysis:

Analysis item: ADRs, etc. corresponding to important identified risks (described in Section 1.4 in Section 1, “Definitions of Terms, etc.”)

Stratification Seriousness [Serious, not serious]

factors:

Analysis methods: For the aforementioned analysis item, analysis will be performed for each stratum by risk as described below. The risks to be analyzed are as described in Section 1.4 in Section 1, “Definitions of Terms, etc.”

[Type of ADR, etc.]

- ADRs, etc. will be coded using the MedDRA/J. ADRs, etc. will be classified by SOC and then tabulated by PT. For the SOC of investigations, ADRs, etc. will be sorted by HLG (lined up in ascending order of HLG code, but not output) and then tabulated by PT.
- For SOC, the number and proportion of patients with an ADR, etc. will be listed in internationally agreed SOC order. Multiple episodes of the same SOC in the same patient will be counted as 1 patient for the relevant SOC. However, when these episodes differ in seriousness, they will be counted once each for “serious” and “not serious.”
- For PT, the number and proportion of patients with an ADR, etc. will be listed in ascending order of PT code. Multiple episodes of the same PT in the same patient will be counted as 1 patient for the relevant PT. However, when these episodes differ in seriousness, they will be counted once each for “serious” and “not serious.”

5.1.6 Occurrence of Adverse Drug Reactions/Infections Corresponding to Important Potential Risks (tabulation by risk)

Patients included in analysis: Safety population

Analysis item: ADRs, etc. corresponding to important potential risks (described in Section 1.4 in Section 1, “Definitions of Terms, etc.”)

Stratification factors: Seriousness [Serious, not serious]

Analysis methods: For the aforementioned analysis item, analysis will be performed for each stratum by risk as described below. The risks to be analyzed are as described in Section 1.4 in Section 1, “Definitions of Terms, etc.”

[Type of ADR, etc.]

- ADRs, etc. will be coded using the MedDRA/J. ADRs, etc. will be classified by SOC and then tabulated by PT. For the SOC of investigations, ADRs, etc. will be sorted by HLG (lined up in ascending order of HLG code, but not output) and then tabulated by PT.
- For SOC, the number and proportion of patients with an ADR, etc. will be listed in internationally agreed SOC order. Multiple episodes of the same SOC in the same patient will be counted as 1 patient for the relevant SOC.

However, when these episodes differ in seriousness, they will be counted once each for “serious” and “not serious.”

- For PT, the number and proportion of patients with an ADR, etc. will be listed in ascending order of PT code. Multiple episodes of the same PT in the same patient will be counted as 1 patient for the relevant PT. However, when these episodes differ in seriousness, they will be counted once each for “serious” and “not serious.”

5.2 Occurrence of Adverse Events and Adverse Drug Reactions/Infections by Seriousness, Time of Onset, and Outcome

5.2.1 Occurrence of Adverse Events by Seriousness, Time of Onset, and Outcome

Patients included Safety population

in analysis:

Analysis item: AEs

Stratification Total

factors:	Seriousness	[Serious, not serious]
	Time of onset	[<7 days, 7-<28 days, 28-<56 days, 56-<84 days, 84-<168 days, >=168 days]
	Outcome	[Recovered, recovering, not recovered, recovered with sequelae, died, unknown, unknown]

Analysis methods: For the aforementioned analysis item, analysis will be performed in each stratum of the stratification factor as described below.

- (1) Number of patients with an AE
- (2) Number of AE
- (3) Proportion of patients with an AE
- (4) Type of AE

For each analysis, events or patients will be counted as described below.

[Number of patients with an AE]

- Number of patients who experienced an AE

[Number of AE]

- Number of reported AE. Multiple episodes of the same AE in the same patient will be tabulated as the total number of episodes.

[Proportion of patients with an AE]

- The proportion of patients with an AE will be calculated as number of patients with an AE/number of patients included in safety evaluation × 100.

[Type of AE]

- AEs will be coded using the MedDRA/J. AEs will be classified by SOC and then tabulated by PT. For the SOC of investigations, AEs will be sorted by HLG (lined up in ascending order of HLG code, but not output) and then tabulated by PT.
- For SOC, the number and proportion of patients with an AE will be listed in internationally agreed SOC order. Multiple episodes of the same SOC in the same patient will be counted as 1 patient for the relevant SOC. Multiple

episodes of the same SOC will be employed as 1 event according to the order of precedence described at the end.

- For PT, the number and proportion of patients with an AE will be listed in ascending order of PT code. Multiple episodes of the same PT in the same patient will be counted as 1 patient for the relevant PT. Multiple episodes of the same PT will be employed as 1 event according to the following order of precedence:

Seriousness: serious → not serious

Time of onset: <7 days → 7-<28 days → 28-<56 days → 56-<84 days → 84-<168 days → >=168 days

Outcome: died → recovered with sequelae → not recovered → recovering → recovered → unknown

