3.2 Rationale

To evaluate potential effects of differences between Leuplin PRO and Leuplin SR, that is, difference amounts of leuprorelin acetate administered in a single dose and different time profiles of serum drug concentration after administration, on the safety, it was decided to investigate the occurrence of injection site reaction and other adverse drug reactions (ADRs) with an incidence of 1% or higher, including the time of onset, incidence, and seriousness.

The sample size of 300 patients was determined to detect ADRs with an incidence of 1% or higher at a probability of 95% or higher.

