9.3 Treatment Given

1) Surveillance items

Treatment status of Leuplin PRO (injection site* and full-treatment status of Leuplin PRO*), treatment status of premenopausal breast cancer drug other than Leuplin PRO (presence or absence and name of the drug), presence or absence of and reason for discontinuation of observation

2) Time points of surveillance

Period from the start of Leuplin PRO treatment to 24 weeks after the start of treatment (or discontinuation of observation)

* At the start of Leuplin PRO treatment

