9.5 Adverse Events (AEs)

1) Surveillance items

Presence or absence of injection site reaction, details of injection site reaction (specific symptom, date of onset, seriousness and reason for seriousness [refer to Table 2]), cause of discontinuation of Leuplin PRO treatment, intervention (presence or absence and contents), date of outcome assessment, outcome, causal relationship to Leuplin PRO [refer to Table 3]).

Presence or absence of AE other than injection site reaction (refer to Table 1), AE term, date of onset, seriousness and reason for seriousness (refer to Table

2), cause of discontinuation of Leuplin PRO treatment, intervention (presence or absence and name of the drug/intervention), date of outcome assessment, outcome, causal relationship to Leuplin PRO* (refer to Table 3)

Patients with “not resolved” or “unknown” outcome or “unevaluable” causal relationship should be followed up wherever possible.

* For the causal relationship to Leuplin PRO, the rationale for “not related” and the reason for “unevaluable” shall be collected.

Note) Additional points to consider for AEs

Abnormal worsening of target disease, for instance, worsening beyond the expected natural course of the disease, will be handled as an AE.

2) Time points of surveillance

Period from the start of Leuplin PRO treatment to 24 weeks after the start of treatment (or discontinuation of observation)

Table 1 Definition of adverse events

An AE is defined as any untoward medical occurrence in a clinical investigation subject administered a drug; it does not necessarily have to have a causal relationship with this treatment. An AE can therefore be any unfavorable or unintended sign (e.g., abnormal laboratory finding), symptom, or disease temporally associated with the use of a drug, whether or not it is considered related to the drug.

The following are also handled as AEs:

- Symptoms and so forth that occur in infants breast-fed by their mothers under treatment with a drug
- Untoward symptoms and so forth that occur in children treated with a drug
- Symptoms and so forth that occur as a result of occupational exposure to a drug
- Symptoms and so forth that occur after administration of counterfeit medicines of our ethical drugs
- Untoward symptoms that have become known to occur in drug users through lawsuits or other legal actions

Table 2 Criteria for assessing seriousness

An AE satisfying any of the following is assessed as serious:

1. Results in death (death)

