1.2 Analysis Sets

The analysis set in this surveillance is safety population. This analysis set is defined as described below.

- Safety population

In this document, the safety population is defined as all Leuplin PRO-treated patients evaluable for safety with no major protocol violation. Patients for whom the CRF has been collected will be excluded from the safety population if any of the following criteria is met:

- Not treated with Leuplin PRO
- Treatment before the contract period
- Registration 15 days or more after Leuplin PRO treatment
- It is unknown whether the patient experienced an AE
- Three-month depot administered

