5.2.2 Occurrence of Adverse Drug Reactions/Infections by Seriousness, Time of Onset, and Outcome

Patients included in analysis: Safety population

Analysis item: ADRs, etc.

Stratification factors: Total

Seriousness	[Serious, not serious]
Time of onset	[<7 days, 7-<28 days, 28-<56 days, 56-<84 days, 84-<168 days, >=168 days]
Outcome	[Recovered, recovering, not recovered, recovered with sequelae, died, unknown, unknown]

Analysis methods: For the aforementioned analysis item, analysis will be performed in each stratum of the stratification factor as described below.

- (1) Number of patients with an ADR, etc.
- (2) Number of ADR, etc.
- (3) Proportion of patients with an ADR, etc.
- (4) Type of ADR, etc.

For each analysis, events or patients will be counted as described below.

[Number of patients with an ADR, etc.]

- Number of patients who experienced an ADR, etc.

[Number of ADR, etc.]

- Number of reported ADR, etc. Multiple episodes of the same ADR, etc. in the same patient will be tabulated as the total number of episodes.

[Proportion of patients with an ADR, etc.]

- The proportion of patients with an ADR, etc. will be calculated as number of patients with an ADR, etc./number of patients included in safety evaluation $\times 100$.

[Type of ADR, etc.]

- ADRs, etc. will be coded using the MedDRA/J. ADRs, etc. will be classified by SOC and then tabulated by PT. For the SOC of investigations, ADRs, etc. will be sorted by HLG (lined up in ascending order of HLG code, but not output) and then tabulated by PT.
- For SOC, the number and proportion of patients with an ADR, etc. will be listed in internationally agreed SOC order. Multiple episodes of the same SOC in the same patient will be counted as 1 patient for the relevant SOC. Multiple episodes of the same SOC will be employed as 1 event according to the order of precedence described at the end.
- For PT, the number and proportion of patients with an ADR, etc. will be listed in ascending order of PT code. Multiple episodes of the same PT in the same patient will be counted as 1 patient for the relevant PT. Multiple episodes of the same PT will be employed as 1 event according to the following order of precedence:

Seriousness: serious \rightarrow not serious

Time of onset: <7 days \rightarrow 7- <28 days \rightarrow 28- <56 days \rightarrow 56- <84 days \rightarrow 84- <168 days \rightarrow ≥ 168 days

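### SAP 5.2.1/5.2.2 divide every time-of-onset window by the full safety population although AE collection stops at discontinuation of observation, so late-window incidence can be understated

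*SAP*

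**What the plan says.** SAP 5.2.1 (AEs) and 5.2.2 (ADRs) stratify by time of onset in six windows: "<7 days, 7-<28 days, 28-<56 days, 56-<84 days, 84-<168 days, >=168 days". Within each stratum the proportion is "number of patients with an AE/number of patients included in safety evaluation", times 100; in 5.2.2 it is "number of patients with an ADR, etc./number of patients included in safety evaluation". The divisor is the same in the first row and the last.

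Observation can end before 24 weeks. Protocol 9.5 collects AEs up to 24 weeks or to discontinuation of observation. SAP 1.2 defines the safety population as "all Leuplin PRO-treated patients evaluable for safety with no major protocol violation" and lists five exclusions. Early end of observation is not among them, and no minimum observation time is set. One exclusion, AE status unknown, will remove some patients who were lost.

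Protocol 9.3 collects "presence or absence of and reason for discontinuation of observation". SAP 4.3 tabulates "Presence or absence of discontinuation of observation" and the reason (failure to attend such as transfer, death, other). That information goes no further: the SAP has no number under observation, person-time rate, cumulative incidence or sensitivity table.

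**The concern.** A patient who transfers elsewhere at week 6 with no AE reported counts as event-free in the 84-<168 day row, although no one was observing her then. With the divisor fixed, events missed after a non-death discontinuation can only lower the printed proportion, and the effect grows with time since injection.

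Timing is part of this surveillance's question. Protocol 2.0 asks whether a larger single amount and a different serum time profile affect safety, Protocol 3.2 names time of onset beside incidence and seriousness, and Protocol 10.6.1 promises incidence by time of onset. A distortion that is nearly nil in week 1 and largest after day 84 falls on the comparison that the onset table exists to support.

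**Working it through.** **The plan's own figure.** Protocol 3.2 chose 300 patients to "detect ADRs with an incidence of 1% or higher at a probability of 95% or higher". The probability of at least one case is 1 − 0.99^300 = 0.951, and the smallest sufficient number is 299. The figure reproduces, with one patient to spare.

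**Inputs.** Observation lasts 24 weeks = 168 days (Protocol 7.1). Onset day = onset date − start date + 1 (SAP 1.5), so the 84-<168 day window runs from 83 to 167 elapsed days. The discontinuation rate d is not in the documents; 5% to 30% is assumed for illustration. Further assumptions: discontinuations are non-death, spread uniformly over 168 days and unrelated to AE risk, and the AE hazard is constant.

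**Formula.** The fraction still observed at elapsed day t is 1 − d·t/168. For uncommon events, printed/true for a window from a to b is about 1 − d·[(a+b)/2]/168.

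- First week (0 to 6, midpoint 3): 1 − 0.018d
- 84-<168 days (83 to 167, midpoint 125): 1 − 0.744d
- Whole 24 weeks (midpoint 84): 1 − d/2

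| d | <7 days | 84-<168 days | 24 weeks |
|---|---|---|---|
| 5% | 0.999 | 0.963 | 0.975 |
| 10% | 0.998 | 0.926 | 0.950 |
| 20% | 0.996 | 0.851 | 0.900 |
| 30% | 0.995 | 0.777 | 0.850 |

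**In absolute terms.** Take a true 24-week incidence P = 10%. The printed figure is (1 − d)P + d·[1 − P/(−ln(1 − P))]. At d = 10% this is 0.090 + 0.10 × 0.0509 = 9.5%; at d = 20%, 9.0%. The true 84-<168 day proportion of 4.87% prints as 4.51% and 4.15%.

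**Timing matters.** If all discontinuations fall before day 84, the late-window shortfall equals d. If events cluster in the first week, the overall figure falls by only about 0.018d, which is 0.2% relative at d = 10%.

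**Effect on detection.** For a 1% ADR with constant hazard, 1 − [1 − 0.01(1 − d/2)]^300 is 94.7% at d = 5%, 94.3% at 10% and 93.4% at 20%, against 95.1% with no dropout.

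**Effect on the shape of the table.** The windows differ in width: 56-<84 covers 28 days and 84-<168 covers 84. At d = 30% with constant low hazard, the late row is proportional to 84 × 0.777 = 65.3 and the row before it to 28 × 0.877 = 24.5, where 0.877 = 1 − 0.3 × 69/168. The ratio is 2.7, against 3.0 with no dropout.

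**The case against.** The strongest reply is that the figures are valid as labelled. The SAP calls them proportions of safety patients with an AE, in a single-arm descriptive surveillance, and does not call them 24-week risks. Patients with unknown AE status are already excluded, and SAP 4.3 shows how many discontinued, so a reader can bound the effect. The shift may also be small against sampling error: at 10% dropout a true 10% prints as 9.5%, while the 95% half-width at 300 patients is 1.96 × √(0.10 × 0.90/300) = 3.4 points. All of this stands, and it limits the point to a conditional one. It does not remove it, because patients with AE status recorded up to departure remain in the divisor, and a table by onset time will be read for timing.

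Some stronger readings are tempting but unsupported:

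- A reader might infer that incidence is understated as a matter of fact. Without a discontinuation rate, only the direction is established.
- A reader might infer that constant risk would appear as declining risk. In the printed rows it would not: unequal widths dominate, and the late row is still the larger one.
- A low count at >=168 days might be blamed on attrition. Under the +1 convention that window covers only the last day or two of observation, so it is nearly empty by design.
- Deaths might be counted among the wrongly retained patients. Keeping them in the divisor is right for a cumulative incidence.
- Protocol 9.3 lists no discontinuation date, but that does not prove none was collected. SAP 5.3.2 tabulates induration size, which Protocol 9.5 does not list either, so the protocol's item lists do not exhaust the CRF.

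**Conclusion.** The point holds in conditional form. The fixed divisor is explicit in both sections, nothing elsewhere in the SAP corrects for truncated observation, and non-death discontinuation can only lower the late-window figures. The main exposure is the 84-<168 day row; overall 24-week incidence is affected less, and hardly at all if events come soon after injection. Below 5% dropout the late-window shortfall is under 4% relative; at 10% it is about 7% and at 20% about 15%. These sizes rest on assumed uniform dropout, constant hazard and dropout unrelated to AE risk. The missing supplement is a cheap improvement; its absence does not invalidate the crude tables.

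**What to change.** Keep the crude tables in 5.1 and 5.2. First establish whether the CRF data hold a discontinuation or last-observation date.

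1. **If a date exists:** print the number under observation at the start of each onset window, and add a 24-week cumulative incidence of first onset with death as a competing event. First onset matches the SAP's precedence rule, which assigns repeat episodes of a term to the earliest window. Plain Kaplan-Meier would censor deaths and could overstate incidence. The window-start count should be shown as context and not used as a new divisor: at d = 30%, 1 − 0.3 × 83/168 = 0.852 are observed at the start of the 84-<168 day window but 0.777 on average, which would leave 1 − 0.777/0.852 = 9% understatement.
2. **If no date exists:** repeat 5.1.2 and 5.2.2 in patients who completed observation plus those whose discontinuation reason was death, using the flags already tabulated in 4.3, and label the result as a sensitivity analysis. Restricting to completers alone would drop patients who died, including any with fatal AEs.

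The cost is one extra table from data in hand. The downside is that the completer-plus-death subset carries its own selection, which the label should state. Adding a date field now is doubtful: the SAP is dated 4 April 2019, and even from the latest registration date in Protocol 8.0 (28 February 2018) 168 days of observation ended in August 2018, so it would mean retrospective queries to about 60 institutions.
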